2.6. Justification of the Dose, Schedule and Route of Administration of TRC105

2.6.1. Phase 1b Justification

The dose and schedule of TRC105 (8 mg/kg weekly up to 10 mg/kg weekly, 15 mg/kg every 2 weeks) for phase 1b were selected based on safety, pharmacokinetics and early evidence of activity in the phase 1 study of TRC105 for patients with solid tumors (Study 105ST101) and in the phase 1b study of TRC105 with bevacizumab. In phase 1, a weekly dose of 10 mg/kg and a dose of 15 mg/kg every two weeks were well tolerated and associated with clinical activity. Dose reduction was possible for treatment of anemia. Doses of 8 and 10 mg/kg TRC105 weekly were tolerated in combination with bevacizumab, pazopanib (dose levels 1 and 2 of this study) and axitinib and doses of TRC105 of 15 mg/kg every 2 weeks were tolerated in combination with sorafenib. Notably, while the initial schedule of TRC105 was adjusted to decrease the frequency of headaches observed with the combination of TRC105 and bevacizumab, there was no potentiation of life threatening toxicities associated with bevacizumab, nor potentiation of common VEGF inhibitor toxicities (e.g., hypertension and proteinuria).

5.3.5.2 Clinical Protocol

Given the limited experience dosing TRC105 with VEGF inhibitors, it is possible that TRC105 toxicities will potentiate pazopanib toxicities, and vice versa. Therefore a TRC105 starting dose of 8 mg/kg weekly, which is 20% lower than the single-agent TRC105 MTD identified in the phase 1 single agent study and phase 1b study with bevacizumab, was selected. In addition a 6 mg/kg (-1) dose level has also been included and will be enrolled should 8 mg/kg of TRC105 in combination with pazopanib exceed the MTD. As an added precaution, the first dose of TRC105 will be delayed by 2 to 4 weeks following pazopanib dosing and administered over 2 days. In addition, pazopanib will be introduced at 800 mg and dose reduced based on patient tolerability over a two to four week period prior to the introduction of TRC105. This administration schedule will limit immediate C_{max} effects of the combination of two drugs that could result in toxicity.

In the phase 1b portion of the study, dose levels 1 and 2, TRC105 at its recommended phase 2 dose of 10 mg/kg given by weekly intravenous infusion was combined safely with pazopanib given at 800 mg p.o. once daily.

The phase 1b portion of the study will also evaluate TRC105 administered every two weeks at 15 mg/kg starting at cycle 2, following initial dosing with 10 mg/kg weekly for the initial 28 day cycle. TRC105 will be given in combination with pazopanib 800 mg daily. In the phase 1 study of single-agent TRC105 (105ST101), TRC105 15 mg/kg administered every 2 weeks was well tolerated and resulted in continuous serum concentrations known to saturate CD105 binding sites on proliferating endothelium. An alternative dosing schedule of every 2 weeks TRC105 treatment in combination with pazopanib, if tolerable, may offer patients more convenience without sacrificing safety and efficacy.

2.6.2. Phase 2 Justification

The Phase 2 portion of the trial is designed to assess the activity of TRC105 in combination with the approved dose of pazopanib, as compared to the single agent activity established for pazopanib in a prior study. Activity of the combination will be assessed as PFS (primary endpoint) and also ORR. Efficacy endpoints will be retrospectively correlated with expression of endoglin on tumor tissue to determine if direct endoglin expression on sarcoma (in addition to the tumor vasculature) may be used as a marker to enrich for responsive sarcoma subtypes in future studies.

Given that the two drugs were well tolerated together at their single agent doses, the phase 2 portion of the study will dose both drugs starting in cycle 1. Dose reductions of pazopanib, based on individual patient tolerability, are permitted starting in cycle 1.

Five patients with cutaneous angiosarcoma were enrolled in the phase 1b/Phase 2 portion of this study and all five patients had tumor reductions, including two patients who progressed on pazopanib prior to trial enrollment. Notably, two patients have ongoing complete responses (at 15 and 22 months of treatment) including one patient who progressed previously after pazopanib and docetaxel. These data were presented at ASCO 2016. Given these signs of activity, two additional phase 2 cohorts of up to 13 patients, each with histologically confirmed angiosarcoma that have progressed following prior systemic treatment, will be enrolled to assess the overall response rate in this subtype of soft tissue sarcoma.

5.3.5.2 Clinical Protocol

Patients in angiosarcoma cohort 1 will initially receive weekly single-agent TRC105 with transition to treatment with the combination of TRC105 and pazopanib at progression per RECIST 1.1.

Patients in angiosarcoma cohort 2 will receive TRC105 in combination with pazopanib starting on cycle 1 day 1.

2.7. Conduct

The 105SAR101 clinical trial will be conducted in compliance with the protocol, GCP, and the applicable regulatory requirements.

5.3.5.2 Clinical Protocol**3. TRIAL OBJECTIVES AND PURPOSE****3.1. Phase 1b Objectives****3.1.1. Purpose**

The purpose of this study is to evaluate the safety and effectiveness of TRC105 in combination with pazopanib.

3.1.2. Primary objectives

- To evaluate safety and tolerability and determine a recommended phase 2 dose for TRC105 when added to standard dose pazopanib in patients with advanced soft tissue sarcoma.

3.1.3. Secondary objectives

- To assess preliminary evidence of improved antitumor activity when TRC105 is added to pazopanib, by assessing response rate and progression-free survival
- To characterize the pharmacokinetic profile of TRC105 when given with pazopanib
- To evaluate the formation of TRC105 anti-product antibodies
- To correlate efficacy with expression of endoglin on sarcoma tissue
- To explore pharmacodynamic effects on circulating angiogenic biomarkers

5.3.5.2 Clinical Protocol**3.2. Phase 2 Objectives****3.2.1. Purpose**

The purpose of this study is to evaluate the safety and effectiveness of TRC105 in combination with pazopanib.

3.2.2. Primary objectives

- To estimate the PFS of patients with advanced soft tissue sarcoma by RECIST 1.1
- To estimate the ORR in a cohort of patients with angiosarcoma by RECIST 1.1

3.2.3. Secondary objectives

- To estimate the ORR in patients with advanced soft tissue sarcoma by RECIST 1.1, including duration of response
- To estimate the PFS in a cohort of patients with angiosarcoma by RECIST 1.1
- To determine the frequency and severity of adverse events as assessed by NCI CTCAE (Version 4.0)
- To characterize the pharmacokinetic profile of TRC105 and pazopanib
- To evaluate the formation of TRC105 anti-product antibodies
- To explore the correlation of efficacy variables (e.g., PFS and ORR) with endoglin expression on sarcoma
- To explore the effects of TRC105 on circulating angiogenic protein biomarkers

5.3.5.2 Clinical Protocol

4. INVESTIGATIONAL PLAN

4.1. Overall Study Design and Plan

4.1.1. Overview

All patients must sign a consent form prior to undertaking any study-related procedures. Prospective patients will be screened to determine if they qualify for the study within 28 days of enrollment. Toxicities will be graded according to the NCI CTCAE Version 4.0.

4.1.1.1. Phase 1b Overview

This is a multicenter, open-label, nonrandomized, phase 1b, dose-finding study of TRC105 in combination with standard dose pazopanib in patients with advanced soft tissue sarcoma. Escalating doses of i.v. TRC105 will be administered weekly or every two weeks beginning with Dose Level 1 in combination with oral pazopanib given as 800 mg p.o. once daily (see TRC105 Administration section 6.1.6 and Pazopanib Dosing section 6.2.5). Intermediate TRC105 doses (below the MTD established during the trial) may be explored based upon clinical, PK, and/or biomarker data.

Dose Level	Number of Evaluable Subjects	Pazopanib mg p.o., once daily (with dose reduction allowed based on tolerability)	TRC105 mg/kg IV
-1	3-6	800	6 (weekly beginning cycle 2 day 1) ^a
1 (Starting Dose)	3-6	800	8 (weekly beginning cycle 2 day 1) ^a
2	3-6	800	10 (weekly beginning cycle 2 day 1) ^a
Expanded Cohort 1	9-12 (up to 15 total at the MTD)	800	MTD (weekly beginning cycle 2 day 1) ^a
3	3-6	800	
 • 10 mg/kg weekly during cycle 1 • 15 mg/kg every two weeks beginning cycle 2 day 1^b
Expanded Cohort 2	At least 6 patients will be treated at the MTD	800	
 • 10 mg/kg weekly during cycle 1 • 15 mg/kg every two weeks beginning cycle 2 day 1^b

^a In dose levels -1 to Expanded Cohort 1, pazopanib will be dosed alone during cycle 1 and dosing with TRC105 will begin on cycle 2 day 1. The first weekly TRC105 dose (cycle 2 day 1) will be split into two doses whereby 3

5.3.5.2 Clinical Protocol

mg/kg is administered on cycle 2 day 1 and the balance (e.g., 5 mg/kg for Dose Level 1) is administered on cycle 2 day 4, the full dose is then given weekly thereafter starting with cycle 2 day 8.

^b In dose levels 3 and expanded cohort 2, pazopanib and TRC105 dosing will begin on cycle 1 day 1. Pazopanib dosing will begin on cycle 1 day 1 and once daily thereafter, and TRC105 will be administered weekly during cycle 1. The first weekly TRC105 dose will be split into two doses whereby 3 mg/kg is administered on cycle 1 day 1 and the balance is administered on cycle 1 day 4. Starting on cycle 2 day 1 and beyond, TRC105 will be administered every two weeks on days 1 and 15 once it is determined that the every two week dosing MTD has not been exceeded.

In dose levels -1, 1, 2 and expanded cohort 1, patients will receive 800 mg of pazopanib daily p.o. in cycle 1, which will be two to four weeks in duration prior to the initial dose of TRC105 given on cycle 2 day 1. Cycle 1 will therefore be as short as 14 days or as long as 28 days, based on the time needed to determine a tolerable dose of pazopanib in each patient. Dose reductions of pazopanib are allowed during cycle 1 based on individual patient tolerability (as well as following cycle 1). TRC105 dosing will begin at 8 mg/kg (Dose Level 1) on cycle 2 day 1. Prior to administration of TRC105 on cycle 2 day 1, all study patients must maintain eligibility criteria indicating adequate organ function, medical status and ECOG performance status (i.e., patients must maintain inclusion criterion #6, 8, 9 and 10 and exclusion criteria #8-21 to continue into cycle 2) and must be able to tolerate pazopanib. A -1 Dose Level has also been included (6 mg/kg) and will be enrolled if 8 mg/kg TRC105 dosed with pazopanib exceeds weekly the MTD. For dose levels -1, 1 and 2, the DLT evaluation period, for purposes of dose expansion, will be the initial 28 days of dosing with TRC105 and pazopanib (from cycle 2 day 1 through cycle 2 day 28). Each cycle will be 28 days in duration.

For dose levels 3, and Expanded Cohort 2, both pazopanib and TRC105 dosing will begin on C1D1 and the DLT evaluation will be the first 28 days of dosing pazopanib with TRC105 every 2 weeks (i.e., from cycle 2 day 1 through cycle 2 day 28). At least 6 patients will be treated at the every two week dosing MTD (or top dose level if a MTD is not determined).

Three patients will be initially enrolled and treated at each dose level. If none of these 3 patients experiences a dose-limiting toxicity (DLT) during the 28-day evaluation period (extending from cycle 2 day 1 until cycle 2 day 28), dose escalation will proceed following review of safety data with site staff including the principal investigators at all sites.

If 1 of 3 patients experiences DLT, the dose level will be expanded to 6 patients. The maximum tolerated dose (MTD) will have been exceeded if $\geq 33\%$ of patients experience DLT at a given dose level. DLT will have occurred when a patient has 1 or more toxicity listed in the table below that is at least possibly related to the combination of pazopanib and TRC105 during the 28 day DLT evaluation period (cycle 2). Patients who exit the study for reasons other than DLT prior to completion of the 28-day DLT evaluation period (cycle 2) will be replaced to ensure an adequate safety assessment in each cohort. Patients who experience DLT who receive less than the prescribed dose of TRC105 or pazopanib due to documented toxicity during the DLT evaluation period will be considered evaluable for dose escalation purposes. A given TRC105 dose level may be reenrolled at $\geq 50\%$ of the pazopanib dose intensity upon agreement of study investigators.

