5.3.5.2 Clinical Protocol

Table 3: Dose Limiting Toxicity Definition and Criteria

Toxicity Category	Drug-Related Toxicity/Grade
Hematologic	Grade 4 neutropenia for ≥ 5 days
	Febrile neutropenia: grade 4 neutropenia with fever > 38.5 °C both sustained over a 24 hour period.
	Neutropenic infection: grade ≥ 3 neutropenia with grade ≥ 3 infection
	Anemia \geq grade 4
	Grade > 4 thrombocytopenia or grade ≥ 3 thrombocytopenia and grade ≥ 3 hemorrhage
Nonhematologic	Grade 3 or 4 nonhematologic toxicity with the following exceptions: 
 • Nausea, vomiting or diarrhea for < 48 hours^a • Asymptomatic electrolyte abnormalities that are corrected to grade 1 or better in < 72 hours^b • headache lasting less than 48 hours

^aPatients with related grade 3 or 4 diarrhea, nausea or vomiting for ≥ 48 hours despite optimal medical therapy will require a one-level dose-reduction of TRC105.

^bPatients with related grade 3 or 4 electrolyte abnormalities that persist for ≥ 72 hours will require a one level dose-reduction of TRC105.

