5.3.5.2 Clinical Protocol

- Upon completion of enrollment of phase 1b dose level 3 and notification by the sponsor, active patients that are past cycle 2, may be switched to an every 2 week dosing schedule at the every 2 week dosing MTD.
- **Phase 1b Dose Levels 3 and Expanded Cohort 2:** TRC105 dosing will start on cycle 1 day 1 and the first dose will be split into two doses whereby 3 mg/kg is administered on cycle 1 day 1, and the balance is administered on cycle 1 day 4. The entire weekly dose of TRC105 (10 mg/kg) is then given on cycle 1 day 8, cycle 1 day 15 and on cycle 1 day 22. Beginning with cycle 2 day 1, TRC105 will be dosed at 15mg/kg and every two weeks thereafter (days 1 and 15).
- **Phase 2 Soft Tissue Sarcoma and Phase 2 Angiosarcoma Cohorts:** TRC105 dosing will start on cycle 1 day 1 and the first dose will be split into two doses whereby 3 mg/kg is administered on cycle 1 day 1, and the balance is administered on cycle 1 day 4. The entire weekly dose of TRC105 (10 mg/kg) is then given on cycle 1 day 8 and weekly thereafter.
 - Upon completion of enrollment of phase 1b dose level 3 and notification by the sponsor, active patients that are past cycle 1, may be switched to an every 2 week dosing schedule at the every 2 week dosing MTD.

TRC105 will be administered intravenously utilizing an infusion pump. TRC105 has been demonstrated to be compatible with polyethylene lined, non-DEHP infusion sets and polyvinyl chloride, non-DEHP infusion sets. TRC105 is required to be administered with a 0.2 micron downstream filter. Duration of infusion administration may be increased as medically necessary.

- Pazopanib dosing. The oral dose of pazopanib is 200 to 800 mg once daily without food (at least 1 hour before or 2 hours after a meal) beginning on cycle 1 day 1 in the absence of toxicity, **except in the phase 2 angiosarcoma cohort 1 where pazopanib will be dosed starting at the time of disease progression on TRC105 single-agent and once daily thereafter in the absence of toxicity.** The dose of pazopanib will not exceed 800 mg and may be reduced based on individual patient tolerability. Do not crush tablets due to the potential for increased rate of absorption which may affect systemic exposure. If a dose is missed, it should not be taken if it is less than 12 hours until the next dose.
- Assessment of adverse events.
- Assessment of concomitant medications and concomitant treatments.

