5.3.5.2 Clinical Protocol

Table 4: Schedule of Assessments Phase 1b Dose Levels -1, 1, 2 & Expanded Cohort 1

Protocol Activities	Screening	Cycle 1 [23]			Cycle 2 [23]				Cycle 3+ [21] [23]				End of Study [3]	28 Day Follow-up [22]
	Day -28	Day 1 [2]	Day 8 (Day 15) (Day 22) [1]	Day 1 [1]	Day 4 [1]	Day 8 [1]	Day 15 [1]	Day 22 [1]	Day 1 [1]	Day 8 [1]	Day 15 [1]	Day 22 [1]		
Baseline Documentation														
Informed Consent [4]	X													
Medical/Oncology History [5]	X													
Baseline Signs and Symptoms [5]	X													
Physical Examination [6]	X	X		X					X				X	
Vital Signs [7]	X	X	X	X	X	X	X	X	X	X	X	X	X	
Laboratory Studies														
Hematology [8]	X+Fe	X+Fe		X+Fe Day -7			X		X		X		X	
Coagulation [8]	X	X		X Day -7										
Blood Chemistry [8]	X+TSH	X+TSH		X+TSH Day -7			X		X + TSH				X + TSH	
Pregnancy Test [9]	Day -7													X
Urinalysis [10]	X	X		X Day -7					X				X	
Treatment w/ Study Drug														
TRC105 Dosing [11]				X Split	X Split	X	X	X	X	X	X	X		
Pazopanib [12]		Daily												
Tumor Assessments														
CT or MRI Scans [13]	X							X				Even Cycles	X	
Other Clinical Assessments														
12-Lead ECG [14]	X		X Day 8				X						X	
Concomitant Medications/Treatments [15]	X	X	X	X	X	X	X	X	X	X	X	X	X	X
Adverse Events [16]		X	X	X	X	X	X	X	X	X	X	X	X	X
Special Laboratory Assessments														
TRC105 PK Pre-Dose [17]							X		Even Cycles					
TRC105 PK Post-Dose [17]							X		Even Cycles				X	X
Anti-product antibodies [18]		X											X	X
Protein Biomarkers [19]		X		X			X		Even Cycles				X	
Archival Tumor Tissue [20]	X													

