5.3.5.2 Clinical Protocol

Table 5: Schedule of Assessments Phase 1b Dose Levels 3 and Expanded Cohort 2

Protocol Activities	Screening	Cycle 1 (10 mg/kg Weekly) [23]					Cycle 2 (15 mg/kg every two weeks) [23]		Cycle 3+ (15 mg/kg every two weeks) [21] [23]		End of Study [3]	28 Day Follow-up [22]
	Day -28	Day 1 [1] [2]	Day 4 [1]	Day 8 [1]	Day 15 [1]	Day 22 [1]	Day 1 [1]	Day 15 [1]	Day 1 [1]	Day 15 [1]		
Baseline Documentation												
Informed Consent [4]	X											
Medical/Oncology History [5]	X											
Baseline Signs and Symptoms [5]	X											
Physical Examination [6]	X	X					X		X		X	
Vital Signs [7]	X	X	X	X	X	X	X	X	X	X	X	
Laboratory Studies												
Hematology [8]	X+Fe	X			X		X	X	X	X	X	
Coagulation [8]	X	X					X				X	
Blood Chemistry [8]	X+TSH	X+TSH					X+TSH		X + TSH		X + TSH	
Pregnancy Test [9]	Day -7						X		X			X
Urinalysis [10]	X	X					X		X		X	
Treatment w/ Study Drug												
TRC105 Dosing [11]		X Split	X Split	X	X	X	X	X	X	X		
Pazopanib [12]		Daily					Daily		Daily			
Tumor Assessments												
CT or MRI Scans [13]	X							X Day 22		Day 22 Even Cycles	X	
Other Clinical Assessments												
12-Lead ECG [14]	X				X						X	
Concomitant Medications/Treatments [15]	X	X	X	X	X	X	X	X	X	X	X	X
Adverse Events [16]		X	X	X	X	X	X	X	X	X	X	X
Special Laboratory Assessments				X							X	
Trough PK [17]		X					X	X	X & Even Cycles	X (Cycle 3 only)	X	X
Anti-product antibodies [18]		X					X		Even Cycles		X	X
Protein Biomarkers [19]		X					X		Even Cycles		X	
Archival Tumor Tissue [20]	X											

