5.3.5.2 Clinical Protocol

Schedule of Assessments Footnotes for Phase 1b Dose Levels 3, 4 and Expanded Cohort 2

1. **Days of Treatment with TRC105:** All assessments should be performed prior to the TRC105 infusion unless otherwise indicated. Each cycle is 28 days in duration.
2. **Cycle 1 day 1:** Hematology (including iron studies), blood chemistry (including TSH testing), urinalysis, physical examination, ECG and pregnancy test not required if acceptable screening assessment is performed within 7 days prior to the start of treatment on cycle 1 day 1.
3. **End of Study:** The end of study visit should generally occur within 14 days (+/- 1 day) of the last dose of TRC105. Assessments other than pharmacokinetics, immunogenicity and protein biomarkers do not need to be repeated if performed within the previous 2 weeks (previous 8 weeks for radiologic tumor assessments). Follow-up visits should occur 28 days following the last dose of TRC105 study drug as outlined in the Schedule of Assessments.
4. **Informed Consent:** Must be obtained prior to undergoing any study specific procedure and may occur prior to the 28-day screening period.
5. **Medical and Oncologic History, Demographics and Baseline Signs and Symptoms:** All information related to prior anticancer treatment should be recorded. Significant medical history and baseline signs and symptoms should be captured from the date of informed consent.
6. **Physical Examination:** Examination of major body systems and ECOG performance status.
7. **Vital Signs:** Heart rate, temperature, blood pressure, respiratory rate, weight. Assessment of vital signs during TRC105 Infusions: Vital signs are to be assessed pre-infusion (i.e., within 30 minutes of starting the infusion) every 30 minutes during the infusion (+/- 15 minutes) and at the end of the infusion (i.e. within 30 minutes after completing the infusion). Vital signs should be monitored more frequently and/or beyond the completion of the infusion if medically indicated (e.g. if the patient experiences an infusion reaction that has not yet resolved).

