8. **Hematology, Chemistry & Coagulation:** Testing to be performed locally. Thyroid stimulating hormone to be tested at screening, day 1 of each cycle and at the end of study visit. Cycle 1 day 1 assessments only need to be performed if screening assessments were performed more than 7 days prior to cycle 1 day 1. Iron studies (FE) to be performed according to the schedule of assessments and as clinically indicated during the study. Thyroid stimulating hormone (TSH) to be performed according to the schedule of assessments and as clinically indicated during the study. Lab assessments may be performed within 3 days prior to TRC105 dosing. In addition to the assessments scheduled for the clinical trial, patients should undergo assessment as appropriate to ensure safe treatment. See Section 8.1.1.1 for specific panel collection requirements.
9. **Pregnancy Test:** Testing to be performed locally. All female patients of childbearing potential must have a negative serum or urine pregnancy test within 7 days of cycle 1 day 1, day 1 of every cycle starting with cycle 2, and 28 days following the last dose of TRC105.
10. **Urinalysis:** To be performed locally. Cycle 1 day 1 urinalysis only needs to be performed if screening urinalysis was performed more than 7 days prior to cycle 1 day 1. Microscopic analysis and/or urine protein creatinine ratio or 24-hour urine protein collection should be performed as clinically indicated.
11. **TRC105 Administration:** Intravenous TRC105 diluted in normal saline will be administered every 7 days during Cycle 1. The first weekly TRC105 dose will be given on cycle 1 day 1 and split into two doses whereby 3 mg/kg is administered on cycle 1 day 1 and the balance is administered on cycle 1 day 4. The entire dose of TRC105 (10 mg/kg) is then given on cycle 1 day 8, cycle 1 day 15 and cycle 1 day 22. Starting on cycle 2 day 1 and beyond, TRC105 will be administered every two weeks on days 1 and 15. See Section 6.1.6 for specific TRC105 administration guidelines.
12. **Pazopanib Dosing:** Oral pazopanib will be dosed once daily at 800 mg starting on cycle 1 day 1 in the absence of toxicity on days 1-28 of each 28 day cycle according to the pazopanib package insert. Dose reductions are allowed based on individual patient tolerability. See Section 6.2 for specific dosing guidelines.

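### For dose level 3 and Expanded Cohort 2, the schedule requires no serum chemistry between the first 15 mg/kg dose and the end of the DLT window

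*Combined protocol and SAP*

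**What the plan says.** For dose level 3 and Expanded Cohort 2, Section 4.1.1.1 states that "the DLT evaluation will be the first 28 days of dosing pazopanib with TRC105 every 2 weeks", and specifies cycle 2 day 1 to day 28. Section 4.1.2.2 puts the first 15 mg/kg dose on cycle 2 day 1 and the second on day 15.

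Table 3 defines nonhematologic DLT as "Grade 3 or 4 nonhematologic toxicity with the following exceptions". One exception is "Asymptomatic electrolyte abnormalities that are corrected to grade 1 or better in < 72 hours". Section 4.1.1.1 treats the MTD as exceeded when 33% or more of patients at a level have a DLT.

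Table 5 marks serum chemistry at screening, cycle 1 day 1, cycle 2 day 1, day 1 of cycle 3 and later, and end of study. Footnote 1 to that table says "All assessments should be performed prior to the TRC105 infusion unless otherwise indicated". Footnote 8 adds "Lab assessments may be performed within 3 days prior to TRC105 dosing", and footnote 23 allows 2 days either side of a visit.

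The table for the weekly dose levels, "Table 4: Schedule of Assessments Phase 1b Dose Levels -1, 1, 2 & Expanded Cohort 1", marks chemistry on cycle 2 day 15.

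**The concern.** A DLT count is only as complete as the tests that feed it. Grade 3 or 4 changes in transaminases, lipase, creatinine or electrolytes can be silent, and are then found only if blood is drawn. The protocol gives reasons to look. Section 6.2.6 sets ALT rules for pazopanib, Section 2.5.1 reports grade 3 pancreatitis with TRC105 plus sorafenib, and Section 2.2.1.3 reports grade 2 creatinine rises with TRC105 plus axitinib.

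The decision at stake is whether the every-two-week MTD has been exceeded. Sections 4.1.1.2, 4.1.2.2 and 6.1.2.2 let active patients move to every-two-week dosing once the sponsor gives notice. The numbers behind that decision are small: 2 of 6 patients with DLT (33.3%) exceeds the MTD and 1 of 6 (16.7%) does not, so one uncounted event can reverse the result.

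**Working it through.** **1. What is scheduled after the first TRC105 dose that opens the window, within cycle 2 days 1 to 28.** Read column by column, for a patient who stays on treatment through cycle 2:

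| Test | Table 4 (weekly levels) | Table 5 (dose level 3, Expanded Cohort 2) |
|---|---|---|
| Serum chemistry | 1 (day 15) | 0 |
| Hematology | 1 (day 15) | 1 (day 15) |
| ECG | 1 (day 15) | 0 (last one is cycle 1 day 15) |

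The blank chemistry cell does not look like a text-extraction fault. The entries agree with footnote 8 to Table 5, which ties TSH to day 1 of each cycle, and the hematology row fills the same day 15 column. Tables 6 and 7 both mark chemistry on cycle 1 day 15, so Table 5 is the only schedule of the four with no day 15 chemistry in any cycle.

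**2. Spacing.** Cycle 2 day 1 (pre-dose) to cycle 3 day 1 is 28 days. The second draw falls on day 29, one day after the window closes. Footnote 8 permits that draw on days 26 to 28, and footnote 23 permits an early visit. Neither requires it.

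**3. Which events escape.**
- Hematologic DLTs are sampled on day 15.
- Symptomatic events should prompt a test.
- A chemistry abnormality still present at cycle 3 day 1 is found, but its onset cannot be placed inside or outside the window.
- A silent abnormality that arises and resolves between the two draws is not found.

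**4. The plan's own figure.** Table 17 follows from P(pass) = (1−p)³ + 3p(1−p)²(1−p)³. At p = 0.30 this is 0.343 + 0.151 = 0.494 (stated 0.49). At p = 0.40 it is 0.216 + 0.093 = 0.309 (stated 0.31). All ten entries reproduce. The formula assumes that every DLT is counted.

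**5. Illustration of undercounting.** Let m be the share of all DLTs not counted. The documents do not give m, so the values below are assumptions. Replace p by q = p(1−m). For p = 0.30 and m = 0.25, q = 0.225, and 0.775³ + 3 × 0.225 × 0.775⁵ = 0.465 + 0.189 = 0.654. Section 10.1.1 requires at least 6 evaluable patients for the MTD, so the table also gives P(at most 1 of 6) = (1−q)⁶ + 6q(1−q)⁵.

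| | m = 0 | 10% | 25% | 50% |
|---|---|---|---|---|
| 3+3 pass, true rate 30% | 0.49 | 0.56 | 0.65 | 0.81 |
| 3+3 pass, true rate 40% | 0.31 | 0.38 | 0.49 | 0.71 |
| At most 1 of 6, true rate 30% | 0.42 | 0.49 | 0.59 | 0.78 |
| At most 1 of 6, true rate 40% | 0.23 | 0.30 | 0.42 | 0.66 |

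Because hematologic and symptomatic DLTs are still seen, m can be no larger than the share of DLTs that are silent and chemistry-only.

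**6. What one day 15 draw could show.** If a proportion p of patients had a chemistry DLT visible on day 15, six patients would show at least one with probability 1 − (1−p)⁶: 0.47, 0.74 and 0.88 at p = 10%, 20% and 30%. These are the complements of the N = 6 row of Table 18 (0.53, 0.26, 0.12). The rates are again assumed.

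**The case against.** The case on the other side is substantial.

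- **Hematology is covered.** Sections 2.2.1.1.3 and 2.2.1.2.1 identify anemia as the toxicity that limited TRC105, and Table 5 samples it on day 15. A reader might infer that laboratory DLTs in general go unseen, and the schedule does not support that.
- **Other routes to detection exist.** Cycle 3 day 1 chemistry comes one day after the window and may be drawn inside it. Footnote 8 and Section 8.1.1.1 allow extra tests, Section 6.2.6 calls for weekly liver monitoring at moderate ALT elevations, and safety data are reviewed before escalation. These routes narrow the gap. They are optional or reactive, though, and a silent event triggers none of them.
- **Prior exposure is reassuring.** Section 2.2.1.4 reports 15 patients at 10 mg/kg weekly with pazopanib and no DLT. Under Table 9, cycle 1 delivers 3 + 7 + 10 + 10 + 10 = 40 mg/kg before the cycle 2 day 1 chemistry, against 15 + 15 = 30 mg/kg in cycle 2. In Table 4 the day 15 sample covers first exposure to TRC105, so the two schedules are not like for like. This lowers the expected yield, but it does not exclude toxicity from the larger single dose, which is what the window is meant to assess.
- **One more draw has limits.** It would be taken before the day 15 infusion, so it informs only on the first 15 mg/kg dose. Nor can a single sample show correction within 72 hours. That exception needs unscheduled repeats under either table.
- **The ECG.** A reader might give the missing cycle 2 ECG equal weight. Table 3 has no ECG-specific criterion, and cycle 1 day 15 keeps the same interval from first TRC105 dose as in Table 4. It is secondary.

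**Conclusion.** The gap is real and narrow. Table 5 requires no post-dose serum chemistry in the 28-day DLT window for dose level 3 and Expanded Cohort 2, where Table 4 requires one sample, and no reason is given. What can be lost is asymptomatic grade 3 or 4 chemistry toxicity that resolves before cycle 3 day 1, or that persists to that visit without a datable onset.

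The size is unknown because the documents do not give the share missed. The probabilities above are illustrations under assumed rates. A reader might set 0.74 with a day 15 draw against nearly zero without one. That contrast holds only if 20% of patients have such an event, it is gone by cycle 3 day 1, and no discretionary test is done. The documents support none of these assumptions.

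A reader might also conclude that DLT rates under the weekly and every-two-week schedules cannot be compared. No such comparison is planned, since each level is judged against its own 33% rule.

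The point concerns the completeness of the DLT count behind the every-two-week MTD. It does not touch the phase 2 PFS or response analyses.

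**What to change.** Reconcile Table 5 with Table 4 and with the DLT window:

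- Mark blood chemistry at cycle 2 day 15 in Table 5.
- State in Section 4.1.1.1 that the pre-dose cycle 3 day 1 chemistry result is reviewed as part of the DLT assessment for dose level 3 and Expanded Cohort 2 before the every-two-week MTD is declared.
- A cycle 2 ECG is optional.

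The cost is a schedule amendment and one extra tube per patient, at a dosing visit where hematology is already drawn, in a small cohort (3 to 6 patients at dose level 3, and at least 6 at the every-two-week MTD). No dose or management rule changes.
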